3.7.2 Adverse events knowing to occur during or after laser procedures

Specific examples of adverse events that potentially may occur during or after laser surgery (regardless of likelihood) include but are not limited to:

- Choroidal hemorrhage
- Choroidal effusion
- Cyclodialysis cleft
- Significant hyphema (i.e. ≥ 10% of anterior chamber)
- Significant iris damage

Possible postoperative adverse events:

- Allergic reaction
- Intraocular inflammation (not pre-existing) remaining or arising after the protocol's specified medication regimen is complete
- Choroidal effusion
- Choroidal hemorrhage
- Aqueous misdirection
- Chronic pain in the study eye present greater than 3 months postoperative
- Clinically significant cystoid macular edema

- Corneal abrasion
- Flat or shallow anterior chamber (e.g., shallowing of the anterior chamber that causes any amount of iris-cornea touch)
- Hypotony (IOP < 6 mmHg) associated with clinically significant findings. (Clinically significant hypotony is defined as hypotony maculopathy or hypotony with flat anterior chamber requiring reformation, corneal folds, choroidal effusions requiring drainage, and/or suprachoroidal hemorrhage)
- Increase in C/D ratio of > 0.3 units
- IOP increase requiring management with oral or intravenous medications or with surgical intervention
- IOP increase ≥ 10 mmHg vs. baseline IOP occurring at any visit
- Iridodialysis
- Loss of best spectacle corrected visual acuity (BSCVA) of 2 lines or more (logMAR scale; 10 letters or more on ETDRS chart)
- Pupillary block
- Secondary surgical intervention
- Significant corneal complications including opacification and decompensation
- Significant corneal edema (NOTE: A classification of mild to moderate corneal edema up to and including the Week 1 postoperative exam is NOT considered an adverse event)
- Significant hyphema (≥ 10% of anterior chamber)
- Vitreous hemorrhage
- Worsening in visual field of mean deviation (MD) of ≥ 2.5 dB compared to the MD used to determine subject eligibility (confirmed in at least 2 out of 3 postoperative visual field tests performed within a 90-day period)

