3.3 Postoperative Instructions

Refer to Appendix B for complete instructions associated with Methods of Clinical Evaluation.

- 1. Following surgery, the investigator or designee will instruct subjects to adhere to the following antibiotic/anti-inflammatory medication regimen for the study eye only:
 - a. Topical antibiotic that is utilized as investigator's routine postop regiments.
 - b. Continuation of glaucoma medications.
- During the study, the discontinuation or a reduction in the dose or frequency of topical IOP lowering medication may be warranted whenever it is in the interest of patient safety.
 Conditions that may warrant discontinuation or frequency reduction in medication include hypotonous condition, an adverse reaction, or other systemic side effect.
- 3. If a pressure rise is observed, a paracentesis may be performed, as necessary. If a paracentesis is performed and there is no protocol-defined adverse event, the paracentesis will be documented in the applicable clinical report form (CRF). If, however, the paracentesis is performed and an anticipated adverse event is determined, then the AE will be recorded, and the paracentesis will be recorded on the applicable CRF as a treatment for the AE.

3.4 Examination Schedule:

Follow-up visits (as shown in Appendix A) will be scheduled over the course of 6 months. A CRF will be completed for each scheduled, unscheduled, and interim exam. Scheduled visits are defined as visits outlined in the schedule of visits. Interim visits are defined as study related visits deemed necessary by the protocol or the PI that are in addition to scheduled visits, and unscheduled visits are defined as visits that are not scheduled or interim. Subjects will be examined and evaluated according to the following scheduled visits:

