3.5 Schedule of Visits and Clinical Assessments

All required clinical assessments should be performed at each scheduled visit as specified in Appendix A. Methods for performing assessments are described in Appendix B.

For interim visits, clinical assessments that are required by the protocol or as deemed necessary by the Investigator will be conducted. Assessments will be performed according to methods described in Appendix B and recorded on an interim visit CRF. Unscheduled visit clinical assessments will be conducted according to standard of care and documented on an unscheduled visit CRF.

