3.7 Adverse Events

3.7.1 Recording Adverse Events

If adverse events (AEs) occur, the first concern will be the welfare of the subject, including any treatment the Investigator believes is appropriate.

Adverse events that occur during the trial whether they are device related or not, will be documented. An adverse event is defined as any **clinically significant** new or changed untoward condition, or a condition requiring treatment, either surgical or medical intervention.

- Recording of all AEs shall include the AE term and assessed relationship of the event to the study device/procedure. Additionally:
 - a. Recording of ocular AEs and related AEs shall include the start and resolution dates, severity, and treatment (if any).
 - b. Recording of non-ocular AEs that are not related to the study treatment will be limited to documenting the start and resolution dates (if any) from subject self- reports or other avenues and no additional information will be recorded.
 - c. All AEs will be documented on the AE CRF.
- 2. Postoperative inflammation within or at 30 days post-surgery will be reported as an AE for cells and flare graded as 3+ or 4+.
- 3. Ocular events occurring greater than 30 days postoperatively that meet the following criteria will be reported as AEs.
 - a. For evaluations for which a standard grading scale is available, ocular AEs will be captured for significant (2-grade) worsening.
 - b. For evaluations where a standard grading scale is not available, clinically significant events assessed as mild, moderate, or severe will be captured as AEs.
- 4. For related, systemic AEs or all ophthalmic AEs treated with surgical intervention, the intervention should be recorded in the Ocular Procedure Log as a treatment for the AE, and the interventional treatment will not be recorded as a separate AE. If a single condition results in multiple protocol defined AE's, the root cause AE will be recorded, and the other events will be recorded as sequelae. (For example, an increase in crystalline lens opacity of greater than 3 half step increments that leads to a VF Mean Deviation loss of greater than 2.5dB. The crystalline lens opacity is recorded as an AE, and the VF Mean Deviation loss is recorded as a sequela).
- 5. The severity (intensity) of AEs will be rated as follows:

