3.9 Statistical Methods

Descriptive statistics will be used for reporting available study results. Baseline and demographic characteristics will be presented. Continuous variables will be summarized by descriptive statistics such as mean, standard deviation, median, minimum, and maximum. Discrete variables will be summarized by frequency tables and percentages.

Adverse events will be summarized by presenting the number and percentage of patients experiencing any adverse event. Any other information collected such as seriousness, severity, and relationship to study device and procedure will be listed as appropriate.

IOP change from baseline will be summarized at each evaluation by mean, standard deviation, and range. Changes in IOP from baseline (Day 0 prior to assigned treatment) will be summarized at each visit. The proportion of subjects with an IOP reduction of 20% or more from baseline will be tallied at each post-operative visit. The number and frequency of medications will be tallied at each visit.

Slit lamp exam and fundus exam findings will be summarized at each visit using frequency and percentage.

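### The listed visual-field adverse event needs two of three fields within 90 days, but only two post-operative fields are scheduled, no repeat is triggered, and the reference mean deviation is unclear

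*Combined protocol and SAP*

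**What the plan says.** **The listed criterion.** Section 3.7.2 gives examples of adverse events in a list introduced with "include but are not limited to". One entry is worsening of MD by at least 2.5 dB. The loss has to be "confirmed in at least 2 out of 3 postoperative visual field tests performed within a 90-day period". The entry fixes the reference value separately, with the phrase "compared to the MD used to determine subject eligibility".

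**Related wording in 3.7.1.** Item 4 explains how to record a root cause and its sequelae. Its example is a lens opacity that "leads to a VF Mean Deviation loss of greater than 2.5dB"; it mentions no confirmation. Item 3b says that, beyond 30 days and where no standard grading scale exists, "clinically significant events assessed as mild, moderate, or severe will be captured as AEs".

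**The schedule.** Appendix A, Table B marks visual fields at Baseline, Month 3 and Month 6 only. Footnote 6 exempts subjects whose screening acuity is 20/100 or worse. Extra visits are possible under 3.4 Examination Schedule: "Interim visits are defined as study related visits deemed necessary by the protocol or the PI". Section 3.5 adds that at these visits "clinical assessments that are required by the protocol or as deemed necessary by the Investigator will be conducted".

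**The reference field.** B.7 says that screening fields decide eligibility, and it accepts one taken within three months of screening. Appendix A places the pre-operative field at Baseline.

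**The analysis.** Section 3.9 summarises continuous variables by mean, SD, median, minimum and maximum. It names per-visit summaries for IOP and medications, and says "Slit lamp exam and fundus exam findings will be summarized at each visit using frequency and percentage". It does not mention visual field by name.

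**Acuity.** Footnote 2 of Appendix A triggers a refraction on a 10-letter loss counted from screening, where footnote 1 specifies a Snellen chart. B.2 counts the same loss from baseline, where acuity is ETDRS. B.2 also places best spectacle corrected acuity at Baseline and Month 6, while Appendix A marks Baseline and Month 12.

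**The concern.** The study's objective is initial evidence of safety, and sections 1.1.3 and 1.5.2 name visual field as a long-term safety outcome. A criterion for reporting field loss should be answerable from the fields the trial performs. Here it asks for three tests in 90 days, and the schedule supplies two over a longer span.

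Two subjects with the same MD loss at Month 3 and at Month 6, both seen within their windows, could be classified differently under 3.7.2 because one had 90 days between visits and the other 91. Two investigators could also differ on whether to arrange a repeat, or on which pre-operative MD to subtract. In a single-arm study of at most 20 subjects, each subject is at least 5 percentage points of any reported rate (1/20).

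**Working it through.** The protocol states no figure for this point, so there is none to reproduce. The inputs are the visit windows (3.4.3 and Appendix A), the field schedule (Appendix A) and the rule in 3.7.2.

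**1. Number of fields.** Two post-operative fields are scheduled (Months 3 and 6). If three tests must be done, scheduled fields can never satisfy the rule.

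**2. Spacing, if two worsened fields suffice.**
- Shortest gap: 168 − 105 = 63 days.
- Longest gap: 196 − 70 = 126 days.
- Gap between window midpoints: 182 − 87.5 = 94.5 days.
- A gap of at most 90 days needs a Month 3 visit on day 168 − 90 = 78 or later. Month 3 visits on days 70 to 77 (8 of the 36 window days) therefore cannot qualify with any in-window Month 6 visit.
- The latest Month 3 day, 105, allows Month 6 up to day 195, which is 28 of 29 window days. No Month 3 day guarantees a qualifying pair.

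For scale only: if all 36 × 29 = 1044 day pairs were equally likely, which is an assumption, 1 + 2 + … + 28 = 406 (38.9%) would be at most 90 days apart. Real visits cluster, so this is not an estimate of what will happen.

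**3. Loss first seen at Month 6.** Ninety days later is day 258 to 286. The next scheduled visit opens on day 330 and has no field. Only an interim field could confirm such a loss.

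**4. Reference MD.** The Baseline field is 3 to 60 days before surgery. An eligibility field accepted under B.7 can be up to about 91 + 30 + 60 = 181 days before surgery (taking three months as 91 days). Inclusion criterion 2 uses the pattern deviation plot or the hemi-field test and sets no MD limit, so it does not identify one MD. Subjects exempt under footnote 6 may have no MD at all.

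**5. Test variability at a 2.5 dB cut-off.** Assume no true change, independent normal test error and a single-test SD s of 1.0 to 2.0 dB. The protocol gives no value for s. The change from Baseline then has SD s√2, and the chance of crossing at a given visit is Φ(−2.5/(s√2)). Two changes sharing one Baseline have correlation 0.5.

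| s (dB) | Crosses at a given visit | Crosses at both | Of 20 subjects: given visit / both |
|---|---|---|---|
| 1.0 | 3.85% | 0.85% | 0.8 / 0.2 |
| 1.5 | 11.9% | 4.2% | 2.4 / 0.8 |
| 2.0 | 18.8% | 8.0% | 3.8 / 1.6 |

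**The case against.** **The rule may be a repeat-test rule.** Two of three within 90 days reads equally well as an instruction for repeat testing once loss is suspected, with interim visits (3.4 and 3.5) supplying the fields. On that reading the Month 3 to Month 6 spacing does not matter, and loss first seen at Month 6 can be confirmed. This stands as a reading. It does not close the gap, because nothing says when a repeat is triggered or how soon it is done, so confirmation is left to discretion.

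**Field loss would not escape reporting.** A reader might infer that loss outside the 90-day span goes unrecorded. The documents do not support that: the list in 3.7.2 is not exhaustive, and 3.7.1 can capture a clinically significant loss by judgement.

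**MD would be summarised.** A reader might also infer that 3.9 leaves visual field unanalysed. It does not. MD is recorded under B.7, and the general sentence on continuous variables covers it. What is missing is the number of subjects who worsened, which a mean, SD and range do not show.

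**Minor wording.** The 3.7.1 item 4 example illustrates sequelae and need not restate the confirmation rule; its strict inequality differs only at exactly 2.5 dB. On the reference MD, section 3.6 lets either screening or baseline criteria decide screen failure, so the Baseline field may itself be the eligibility field. The ambiguity arises only where an earlier field also exists.

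**Conclusion.** The point holds in limited form. As written, the listed criterion cannot be met on scheduled fields if three tests are required, and is date-dependent if two suffice; otherwise it depends on interim fields that no section triggers. The consequence is inconsistent classification of a named safety outcome, not certain loss of events. It probably affects few subjects, since the date dependence matters only for those worsened at both visits. The protocol gives no basis for estimating how many have true loss.

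The counts of fields and the 63 to 126 day span follow directly from the schedule and need no assumption. Any percentage of qualifying visit pairs rests on an assumed pattern of visit dates and should not be quoted as an expected rate. The acuity inconsistencies are separate. The choice between a Snellen and an ETDRS reference affects a measurement trigger, while the Month 6 versus Month 12 entry is a wording error, since B.2 itself defers to Appendix A.

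**What to change.** 1. **Section 3.9.** Tabulate n and % with MD worsening of at least 2.5 dB from the scheduled Baseline field, at Month 3 and at Month 6, among subjects with both the Baseline field and the field at that visit. Split the worsened subjects into those seen at one visit and those seen at both. State how many subjects are exempt under footnote 6 and how many lack a field. This uses data already scheduled and depends on neither visit spacing nor discretionary repeats. The cost is that some counted changes will be test variability, on the scale shown in the table above; the split lets readers judge this.

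2. **Sections 3.7.2, 3.7.1 item 4, Appendix A and B.7.** Reconcile them so that there is one threshold, one reference MD, and a confirmation criterion that the fields performed can answer. The sponsor can align the criterion with the scheduled fields, or keep two of three within 90 days and state when repeat fields are done. The first adds no tests but leaves loss first seen at Month 6 unconfirmed. The second can confirm it but adds fields to the schedule.

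3. **Appendix A footnote 2 and B.2.** Reconcile the 10-letter trigger on the Baseline ETDRS letter score, and make B.2's visit for best spectacle corrected acuity agree with Appendix A. Because habitual-correction acuity would then be compared with a best-corrected baseline, some extra refractions may follow.

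Items 1 and 3 are changes of wording plus one table. Item 2 is wording only unless the repeat-field option is chosen.

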3.7.3 Serious Adverse Events (SAES)

Serious adverse events are defined as any findings that suggest a significant hazard, contraindication, side effect, or precaution. Any adverse event is considered a serious adverse event if it results in any of the following outcomes:

- Death
- Life- or sight-threatening
- Overnight hospitalization or prolongation of an existing hospitalization
- A persistent or significant disability or incapacity
- A congenital anomaly or birth defect

The terms "mild," "moderate", and "severe" are measures of intensity; thus, a severe AE is not necessarily serious. For example, nausea of several hours duration may be rated as severe but may not be clinically serious.

Important medical events that may not result in death, be life-threatening, or require overnight hospitalization may be considered a serious adverse experience when, based upon appropriate medical judgment, they may jeopardize the subject and may require medical or surgical intervention to prevent one of the outcomes listed above. A life-threatening event is any event that places the subject at immediate risk of death from the event as it occurred; it does not refer to an event that hypothetically might have caused death if it were more severe. A sight- threatening event is any event that places the subject at immediate risk of permanently losing vision in either eye as a direct result of the event.

Serious, alarming, and/or unusual adverse events must be reported to ViaLase within 24 hours of the investigator's knowledge of the event:

[contact]

[contact]

Email: [contact]

An AE Form and supplemental SAE Report Forms must be completed as much as possible for all serious adverse events and faxed to ViaLase within 24 hours of knowledge of the event.

When new significant information (including the outcome of the event) is obtained, the investigator should inform ViaLase by telephone, facsimile, or email as soon as possible. Depending on the nature and seriousness of the AE, ViaLase may request copies of the ophthalmic and medical record of the subject as well as results of laboratory tests. If the subject was hospitalized, a copy of the discharge summary must be forwarded to ViaLase as soon as possible.

Sight-threatening AEs include but are not limited to events such as endophthalmitis and corneal decompensation, severe retinal detachment, severe choroidal hemorrhage, severe choroidal detachment, and aqueous misdirection.

Sight-threatening AEs will be reported to ViaLase and to the Investigator's IRB as soon as possible, but in no event later than 10 working days after the Investigator first learns of the event. Subjects who are terminated from the study due to adverse experiences will be followed until their medical outcome is determined; written reports will be provided to the ViaLase Clinical Research Department by the Investigator.

3.7.4 Unanticipated Adverse Device Effect

Unanticipated adverse device effect (UADE) is defined as any serious adverse effect on health or safety or any life-threatening problem or death caused by, or associated with, a device, if that effect, problem, or death was not previously identified in nature, severity, or degree of incidence in the investigational plan or application (including a supplementary plan or application), or any other unanticipated serious problem associated with a device that relates to the rights, safety, or welfare of subjects. Date and time of the event, its severity, treatment if any, and the assessed relationship of the event to the study device will be recorded on the AE form.

Unanticipated adverse device effects must be reported to ViaLase and to the Investigator's IRB as soon as possible, but in no event later than 10 working days after the Investigator first learns of the event. Subjects who are exited from the study due to unanticipated adverse device effects will be followed until their medical outcome is determined; the Investigator must provide written reports to the ViaLase Study Manager.

3.7.5 Follow-up after Adverse Events

Related systemic and all ophthalmic AEs for either eye at any level of potential relatedness (unlikely related, possibly related, probably related, or definitely related) will be followed and documented until complete resolution, resolution with sequelae, until the subject exits from the study for conditions with no possibility of resolution (e.g., iris atrophy, macular degeneration), or for one month after study exit.

Subjects with AEs will continue to be followed according to the protocol, unless continuing to do so would place the subject at undue risk (e.g., if they are hospitalized).

If a subject requires additional glaucoma surgery, the subject will continue to be seen for the duration of the study at required follow-up visits so that safety and effectiveness can continue to be monitored.

3.8 Source Documentation and Data Reporting

A Case Report Form booklet will be provided by ViaLase for each subject enrolled in the study. The appropriate Case Report Form will be completed at each examination. The original forms, not copies, will be returned to the sponsor along with an affidavit of obtaining signed Informed consent. Copies will be retained by the site.

ViaLase personnel will monitor all clinical studies in a manner consistent with applicable health authority regulations and the clinical research standards adopted by ViaLase, Inc.

3.9 Statistical Methods

Descriptive statistics will be used for reporting available study results. Baseline and demographic characteristics will be presented. Continuous variables will be summarized by descriptive statistics such as mean, standard deviation, median, minimum, and maximum. Discrete variables will be summarized by frequency tables and percentages.

Adverse events will be summarized by presenting the number and percentage of patients experiencing any adverse event. Any other information collected such as seriousness, severity, and relationship to study device and procedure will be listed as appropriate.

IOP change from baseline will be summarized at each evaluation by mean, standard deviation, and range. Changes in IOP from baseline (Day 0 prior to assigned treatment) will be summarized at each visit. The proportion of subjects with an IOP reduction of 20% or more from baseline will be tallied at each post-operative visit. The number and frequency of medications will be tallied at each visit.

Slit lamp exam and fundus exam findings will be summarized at each visit using frequency and percentage.

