APPENDIX A – SCHEDULE OF VISITS AND CLINICAL ASSESSMENTS

Table B – Table of Scheduled Visits and Clinical Assessments

Visit Windows	Screening	Baseline	Operative Day 0	Day 1	Week 1	Month 1	Month 3	Month 6	Month 12
Window Range	1-30 days before Baseline	3-60 days before Operative	3-60 days after Baseline	1-day post-op	5-9 days post-op	21-35 days post-op	70-105 days post-op	168-196 days post-op	330-420 days post-op
Informed Consent	Х								
Demographics	Х								
Ocular History	Х								
Ocular Medication Assessment	Х	Х		Х	Х	Х	Х	Х	Х
Medical History	Х								
Medication Assessment	Х	Х		Х	Х	Х	Х	Х	Х
Pinhole VA (Snellen)				Х	Х				
Corrected VA (CVA)	X ¹			Х	Х	X ²	X ²	X ²	Х
Manifest Refraction		Х							Х
Best Spectacle Corrected VA (ETDRS)		Х							Х
Endothelial Cell Density		X				Х		Х	X
Slit Lamp Exam ³	Х			X	X	X	X	Х	X

 $^{^{\}rm 1}$ Snellen chart will be used for assessing corrected VA at the Screening visit.

² ETDRS chart will be used for assessing corrected VA at Months 1, 3 and 6. If corrected VA indicates a greater than or equal to 10 letter loss from screening, a refraction should be performed followed by a best spectacle corrected VA assessment using an ETDRS chart.

³ Slit lamp exam includes lenticular opacity grading.

Visit Windows	Screening	Baseline	Operative Day 0	Day 1	Week 1	Month 1	Month 3	Month 6	Month 12
Window Range	1-30 days before Baseline	3-60 days before Operative	3-60 days after Baseline	1-day post-op	5-9 days post-op	21-35 days post-op	70-105 days post-op	168-196 days post-op	330-420 days post-op
IOP via Goldmann Applanation Tonometry	Х		X ⁴	Х	X	Х	Х	Х	
Diurnal IOP via Goldmann Applanation Tonometry (8:00 am, 12:00pm, and 4:00 pm)		Х					Х		Х
Gonioscopy	Х				X	X	X	X	X
Dilated Fundus Exam ⁵	Х					Х	Х	Х	Х
Visual Field ⁶		Х					Х	Х	
Pachymetry	Х							Х	Х
Ocular Biometry	Х								
Surgery			Х						
Adverse Event Assessment	Х	Х	Х	Х	Х	Х	Х	Х	
Exit									Х

⁴ IOP will be assessed after surgery on Day 0 and can be done at any time per investigator discretion

⁵ Includes vertical C/D ratio assessment.

⁶ Subjects with a visual acuity at screening of 20/100 or worst are not required to have a visual field performed.

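### The one adverse event percentage in section 3.9 pools pre-laser, fellow-eye and unrelated events with study-eye events after the laser, and no section splits AEs by eye, onset or event term

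*Combined protocol and SAP*

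**What the plan says.** Section 3.9 (Statistical Methods) sets the AE summary in two sentences. The first is "Adverse events will be summarized by presenting the number and percentage of patients experiencing any adverse event". The second is "Any other information collected such as seriousness, severity, and relationship to study device and procedure will be listed as appropriate". The section also has a general rule, "Discrete variables will be summarized by frequency tables and percentages", and one for examination findings, "Slit lamp exam and fundus exam findings will be summarized at each visit using frequency and percentage". None of these mentions study eye versus fellow eye, onset before or after the laser, or AE term.

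Other sections determine what enters the count:

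- **Unrelated events.** Section 3.7.1: "Adverse events that occur during the trial whether they are device related or not, will be documented". For unrelated non-ocular illness the detail is reduced, but the event is still recorded: "Recording of non-ocular AEs that are not related to the study treatment will be limited to documenting the start and resolution dates".
- **The untreated eye.** Section 3.7.5 follows "Related systemic and all ophthalmic AEs for either eye at any level of potential relatedness", while section 1.4 has one eye treated per subject.
- **The period before the laser.** In Appendix A, Table B, the row "Adverse Event Assessment" is marked at Screening and Baseline as well as from Day 0 on.

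Two sections bear on the point from the other side. Section 1.5.1 defines percentages for five early findings over Day 0, Day 1 and Week 1: IOP elevation at 1 hour, iritis with flare and cells, hyphema, corneal haze and hypotony. Section 1.5.3 (repeated in the synopsis) commits to tabulating and analysing all AEs by seriousness, severity, outcome, relationship to device and relationship to procedure.

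**The concern.** The stated objective is initial evidence of safety, so the AE summary reports on the main purpose of the study. Under the wording of 3.9, a patient counts once for any event. A treated systemic illness before surgery, an event in the untreated eye and a choroidal hemorrhage in the lasered eye each add the same one to the numerator. The resulting percentage mixes background morbidity in people aged 45 or older with harm from the laser. The higher the background, the less the figure moves when the laser causes harm.

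The denominator is also unsettled. Section 3.1 treats a subject as enrolled at consent and section 3.6 at surgery, so pre-laser events in screen failures could fall in or out of the table.

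**Working it through.** The plan gives no AE rate, power or precision figure to reproduce. The check asks how far the pooled percentage can depart from the study-eye rate.

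**Inputs from the documents**

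- Screening is 1 to 30 days before Baseline and Baseline is 3 to 60 days before surgery. Screening to laser is therefore 1 + 3 = 4 to 30 + 60 = 90 days.
- Follow-up is nominally 12 months (365 days), giving 365 + 4 = 369 to 365 + 90 = 455 days in total.
- The AE row of Table B, as extracted, has no mark at Month 12. If collection stops at Month 6 (168 to 196 days), the total is 4 + 168 = 172 to 90 + 196 = 286 days. Section 1.5 says safety is assessed over 12 months, so both cases are shown.
- At most 20 subjects are consented.

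**Assumptions, not in the documents**

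- Background AEs (non-ocular plus fellow-eye) occur at a constant 0.3 to 1.0 per patient-year.
- A study-eye laser AE occurs independently in 15% of patients.

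**Formulas**

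- Background risk: b = 1 − exp(−rate × days / 365.25)
- Pooled risk with laser risk l: 1 − (1 − b)(1 − l)
- Points added by the laser: l(1 − b)

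| Collection | Rate | Days | b | Pooled with l = 15% | Points added |
|---|---|---|---|---|---|
| To Month 12 | 0.3 | 369 | 26.1% | 37.2% | 11.1 |
| To Month 12 | 1.0 | 455 | 71.2% | 75.5% | 4.3 |
| To Month 6 | 0.3 | 172 | 13.2% | 26.2% | 13.0 |
| To Month 6 | 1.0 | 286 | 54.3% | 61.2% | 6.9 |

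For example, in the second row 1.0 × 455 / 365.25 = 1.246, exp(−1.246) = 0.288, b = 71.2%, and 0.15 × 0.288 = 4.3 points.

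**Precision at n = 20.** Take b = 50% and l = 20%. The pooled risk is 1 − 0.5 × 0.8 = 60%, or 12 of 20. The exact 95% interval for 12/20 is 36.1% to 80.9%, which contains the 50% expected with no laser harm. A table restricted to study-eye events after the laser estimates l directly: 0/20, for instance, has an exact 95% interval of 0 to 16.8%.

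**Share from the pre-laser period.** Relative to the Month 12 window of 330 to 420 days, it is 4/(4 + 420) = 1% to 90/(90 + 330) = 21% of observation time. It is a minor to moderate contributor.

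**Does another section supply the split?** The breakdown in 1.5.3 names neither eye, nor onset, nor event term. Relationship does not stand in for them. Section 3.7.1 leaves it to the investigator's judgement, and its possibly-related category admits events for which another cause seems more likely. Every category also refers to study testing, so an event caused by a pre-laser test could be classed as related. The percentages in 1.5.1 end at Week 1 and cover five findings. Several events listed in 3.7.2, such as loss of two or more lines of BSCVA, cyclodialysis cleft, cystoid macular edema and secondary surgical intervention, have no percentage of their own.

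**The case against.** The strongest reply is that 3.9 should not be read alone. Section 1.5.3 already promises tables by relationship to device and procedure, which would separate most unrelated illness. Relationship and severity are discrete variables, so the general rule in 3.9 could be read to give them percentages. Section 1.5.1 reports key early laser effects directly, and slit lamp and fundus findings get percentages at each visit. With at most 20 patients, and with term, relationship and dates recorded, a serious study-eye event would be visible in a listing. All of this stands, and it limits the consequence.

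Three stronger readings are tempting, and the documents do not support them:

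- **That background illness will swamp or hide the laser signal.** The outputs just named are free of most of that background. At the low assumed rates the laser still adds 11 to 13 of its 15 points; the 4-point figure is the least favourable corner of the range. The AE definition also requires clinical significance or treatment, so trivial illness need not enter.
- **That any-AE is the principal safety outcome.** No section says so.
- **That the fellow eye is a within-patient control.** The exclusion criteria apply to the study eye only, so the fellow eye may have had surgery, inflammation or cataract.

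The reply leaves one gap: no section specifies a split by eye, by onset relative to the laser, or by event term.

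**Conclusion.** The point holds in a limited form. The only AE percentage named in 3.9 does not estimate study-eye harm after the laser and can understate the laser's contribution. Under the assumed rates, a 15% laser risk appears as an increase of about 4 to 13 points. That range rests on the assumed background of 0.3 to 1.0 AEs per patient-year, on independence, and on whether AE collection ends at Month 6 or Month 12. The lack of a split by eye, onset or term does not depend on these assumptions. Nor does the conflict between 3.9, which leaves seriousness, severity and relationship to listings, and 1.5.3, which promises tabulation. This should be corrected because safety is the objective and the change is cheap. It does not show that laser harm would go unseen.

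**What to change.** In section 3.9:

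1. Make the main AE table the number and percentage of treated subjects with study-eye AEs whose onset is at or after the start of the laser procedure, by event term.
2. Carry through the breakdown promised in 1.5.3 (seriousness, severity, outcome, relationship to device and to procedure) as tables, so that the two sections agree.
3. Show fellow-eye AEs, non-ocular AEs and AEs with onset before the laser in separate descriptive tables, with the fellow eye as context and not as a control.
4. Keep any-AE as a final line, and state the denominator, given the two definitions of enrollment in 3.1 and 3.6.
5. State whether AE collection runs to Month 6 or Month 12, and align Table B with section 1.5.

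The cost is table programming. Start dates are already collected. Eye is not among the AE items named in 3.7.1, so confirm that the AE form records it and add the field if it does not. No visits or tests are added.
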